### **2.3. Baseline Definition**

In general, for questionnaire data, baseline is defined as the assessment completed during Stage 1 of the study on Day 0 (as indicated in Table 1).

For the sleep diary, baseline will be considered the assessment completed on Day 0 of Stage 2 (as indicated in Table 1).

Change from baseline variables will be calculated as:

- post-treatment value minus the value at baseline.

If applicable, % change from baseline will be calculated as:

- (post-baseline value - baseline value)/baseline value x 100.

### **2.4. Study Day**

For Stage 1, Study Day 0 will be defined as the day that the questionnaires (ISI, EQ-E5-DL, FACT-ES) are completed. This will be referred to as S1D0, for Stage 1 day 0. All questionnaires are expected to be completed on the same day but if any are completed after day 0 then they will be labelled accordingly relative to day 0 (e.g. S1D2, if done 2 days after the initial day 0).

For Stage 2, Study Day 1 will be defined as the first day the sleep diary is completed in Stage 2 and will be referred to as S2D1. All subsequent assessment will then follow in sequence as S2D2, S2D3, S2D4 etc.

### **2.5. Missing Data Handling Rules**

In general, other than for partial dates, missing data will not be imputed and will be treated as missing. Where applicable, outcomes may still be derived for questionnaire data based

Statistical Analysis Plan for CLM-INS-004

Version: Final 2.0

Date: 9th September 2022

on missing data rules. For example, FACT scores can still be derived provided <50% of data is missing. Any missing data rules are provided in the relevant derivation sections.

Where applicable missing categories will be presented to show the number of patients with missing data for the relevant endpoint.

Imputation of partial dates

*Initial diagnosis date:*

- If year is missing, do not impute.
- If only day is missing, impute day as 15th of the month.
- If day and month are missing, impute as July 1st.

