6 PARTICIPANT ELIGIBILITY CRITERIA

6.1 Inclusion criteria

To be eligible to participate in Stage 1, the following criteria must be met:

1. Age ≥ 18 years.
2. Informed consent to Stage 1 of the study.
3. Diagnosis of Stage I, II or III Breast Cancer within the previous 12 months.

To be eligible for Stage 2 of the study, the following criteria must be met:

1. Informed consent to Stage 2 of the study.
2. Current Sleep Disturbance; a score of 8 or more on the Insomnia Severity Index.
 - Total ISI score categories: 0–7 = No clinically significant insomnia
8–14 = Subthreshold insomnia
15–21 = Clinical insomnia (moderate severity)
22–28 = Clinical insomnia (severe)
3. History of sleep disturbance prior to the screening/baseline consultation; with beginning or worsening of sleep disturbance since breast cancer diagnosis e.g. sleep problems began or get worse with the diagnosis of breast cancer or with chemotherapy.
4. Possession of a suitable smartphone that participant can use independently.

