7.1 Recruitment

Recruitment will take place at the Christie NHS Foundation Trust over a four-month period and is planned to end (last participant enrolled) by January 2022.

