10.2 Planned recruitment rate

Recruitment will take place over a four-month period and is planned to end (last participant enrolled) by January 2022. Expected recruitment rate for Stage 1 is aimed at 15 participants per week with approximately half of these (7-8 participants per week) being eligible for Stage 2 of the study.

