# 1. INTRODUCTION

The purpose of this statistical analysis plan (SAP) is to provide detailed descriptions of the planned analysis and reporting of the data from the study CLM-INS-004 (Protocol version 1.0 dated 28th September 2021).

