### **3.1.4. Medical History of Breast Cancer**

The following will be summarized for the stage 2 analysis set only.

- Time since breast cancer diagnosis (derived as consent date-diagnosis date+1)
- Stage of disease (Stage I to Stage III)
- Tumor staging (T1, T2, T3, T4, DCIS)
- Nodes staging (N0, N1, N2, N3)
- Surgery type (Lumpectomy, Mastectomy, Double Mastectomy, No surgery, Not available)

Statistical Analysis Plan for CLM-INS-004

Version: Final 2.0

Date: 9th September 2022

- Time since surgery (derived as consent date-surgery date+1, for applicable patients)
- Neoadjuvant treatment (Y/N)
- Oestrogen receptors (Y/N)
- Progesterone receptors (Y/N)
- HER2 receptors (Y/N)

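### The rules for partial diagnosis dates have no bound at consent or at the 12-month window, so year-only 2020 and 2022 dates give impossible times since diagnosis

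*SAP*

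**What the plan says.** SAP 2.5 gives two working rules for an incomplete initial diagnosis date: "If only day is missing, impute day as 15th of the month" and "If day and month are missing, impute as July 1st". A date with no year is left alone. The section does not mention the consent date or the eligibility window as a limit on the imputed date.

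The date feeds one variable in SAP 3.1.4: "Time since breast cancer diagnosis (derived as consent date-diagnosis date+1"). That section opens with "The following will be summarized for the stage 2 analysis set only".

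Three other statements fix which dates are possible:

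- Protocol 6.1 requires "Diagnosis of Stage I, II or III Breast Cancer within the previous 12 months".
- Protocol 10.2 states "Recruitment will take place over a four-month period and is planned to end (last participant enrolled) by January 2022".
- SAP 1 ties the plan to "Protocol version 1.0 dated 28 th September 2021", so consent before that date is not expected.

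**The concern.** The first of July is a reasonable guess when any day of the year is possible. Here it is not. Diagnosis must lie in the 12 months before entry, and entry was planned over four months around the turn of 2021 to 2022. Only the last months of 2020 and the first weeks of 2022 can then contain an eligible diagnosis, and 1 July lies in neither.

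At stake is the credibility of one reported variable. A patient correctly enrolled within 12 months would be shown with a time since diagnosis of 15 months or more, or with a negative time. SAP 2.1 asks for the minimum and maximum of continuous variables and for full listings, so one such record would show in the range.

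**Working it through.** The documents give no figure for this point, so there is nothing to reproduce. The check is date arithmetic.

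**Inputs.** Consent: 1 October 2021 to 31 January 2022, a reading of the planned four months. Eligible diagnosis: from the same calendar date one year earlier up to the consent day. Imputed date for a year-only record: 1 July of that year. Time since diagnosis = consent date - diagnosis date + 1, so a diagnosis on the consent day scores 1, and 0 or less means a date after consent.

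**Year 2020.** A 2020 diagnosis is feasible for consent from 1 October to 31 December 2021.
- Consent 1 October 2021: 365 + 92 + 1 = 458 days.
- Consent 31 December 2021: 365 + 183 + 1 = 549 days.
- Every value exceeds 12 months. True dates run from 1 October to 31 December 2020, so the time is overstated by 92 to 183 days.

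**Year 2021.** Values run from 92 + 1 = 93 to 214 + 1 = 215 days, always inside the window.

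**Year 2022.** A 2022 diagnosis is feasible for consent from 1 to 31 January 2022.
- Consent 1 January: -181 + 1 = -180 days.
- Consent 31 January: -151 + 1 = -150 days.
- Every value is negative.

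**Share of feasible diagnoses in the failing years.** Assume consent and diagnosis dates are uniform. There are 123 consent days with 366 possible diagnosis days each: 123 × 366 = 45,018 pairs.
- 2020: 92 + 91 + ... + 1 = 4,278 pairs, 9.5%.
- 2022: 1 + 2 + ... + 31 = 496 pairs, 1.1%.
- Together: 4,774 / 45,018 = 10.6%.

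**Sensitivity to the assumed dates.**

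| Consent period | 2020 (days) | 2022 (days) | Inadmissible share |
|---|---|---|---|
| 1 Oct 2021 to 31 Jan 2022 | 458 to 549 | -180 to -150 | 10.6% |
| 28 Sep 2021 to 31 Jan 2022 | 455 to 549 | -180 to -150 | 11.0% |
| 1 Oct to 31 Dec 2021 | 458 to 549 | none feasible | 12.7% |
| 1 Oct 2021 to 28 Feb 2022 (Stage 2 consent, up to 28 days later) | 458 to 549 | -180 to -122 | 10.9% |
| 1 Oct 2021 to 30 Jun 2022 (overrun, assumed) | 458 to 549 | -180 to 0 | 20.8% |
| 1 Oct 2021 to 31 Aug 2022 (overrun, assumed) | 458 to 549 | -180 to 62 | 24.5% |

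In the last row some 2022 imputations become admissible (55.6% still fail) and some 2021 ones stop being so (10.5% fail).

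**Day-15 rule.** If diagnosis and consent fall in the same month and consent is on day 1 to 14, the value lies between 1 - 15 + 1 = -13 and 14 - 15 + 1 = 0. Example: diagnosis 2 November 2021, consent 8 November, day missing: 8 - 15 + 1 = -6. At the other end, diagnosis 25 November 2020 with consent 20 November 2021 becomes 15 November 2020: 370 + 1 = 371 days, just outside the window.

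**The case against.** The strongest reply is that the rule will hardly ever be used. Eligibility is checked from patient records (Protocol 7.2), and a bare year of 2020 cannot confirm diagnosis within 12 months, so the site would normally need at least the month. A January 2022 diagnosis would be only days or weeks old at consent, and a year-only record of it at the treating centre is hard to imagine. Protocol 11.4 and 11.5 add entry checks, queries and investigator sign-off. All this stands. The documents give no count of partial dates, and very few should be expected. It does not make the rule right when it applies, and the sponsor thought partial dates likely enough to write a rule for them.

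A second reply is that the dates are planned ones. The SAP is dated September 2022 and reports no actual recruitment dates. This also stands. If nobody consented in January 2022, the 2022 case disappears; if consent ran past 1 July 2022, the pattern changes. The 2020 failure remains in every scenario tabulated.

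Two stronger readings are tempting, and neither is supported. Failure in two of three calendar years might be taken to mean most patients; the share is about 11% of feasible diagnoses, and only among records lacking both day and month. A reader might also infer that an imputed date could remove a patient from an analysis set, because SAP 2.2 limits both sets to eligible participants. Nothing in SAP 2.2 refers to imputed dates. Eligibility is judged by the clinical team from records (Protocol 7.2 and 7.4.1), and cancer history is captured only after Stage 2 consent (Protocol 7.4.4), so it could not define the Stage 1 set.

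**Conclusion.** The point holds, and it is minor. As written, the year-only rule gives an inadmissible date for every feasible 2020 diagnosis and, on the planned dates, for every feasible 2022 diagnosis. The day-15 rule can miss by up to about two weeks below zero.

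The reach is one descriptive variable in the Stage 2 set. Even if every one of the 125 patients expected to be eligible for Stage 2 had a year-only date, uniform dates would put about 0.106 × 125 = 13 of them in a failing year; the real number should be far smaller. The primary prevalence estimate (SAP 3.2.1) does not use the date. Nor do the subgroups in SAP 3.6, where prior chemotherapy is timed from its own start.

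The day ranges rest on the planned recruitment period, and the 11% also on uniform dates. SAP 3.1.4 does not say whether Stage 1 or Stage 2 consent is meant; the conclusion is the same either way.

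**What to change.** Add to SAP 2.5, in place of the two fixed dates:

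> The imputed date is the midpoint of the part of the known month or year that lies between consent minus 12 months and consent; if no part of the known month or year lies in that interval, the date is queried and left missing. Imputed dates are used for this summary only.

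Say in the same place which consent date applies.

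Effect on two examples:
- Consent 15 November 2021, year 2020: the feasible part is 15 November to 31 December 2020, midpoint 8 December, giving 342 + 1 = 343 days instead of 503.
- Consent 20 January 2022, year 2022: the feasible part is 1 to 20 January, midpoint about 10 January, giving 10 + 1 = 11 days instead of -161.

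Capping at consent alone would remove the negative values but leave the 2020 error. The lower bound does build the inclusion criterion into the imputed value, which is why the text needs its fallback and its restriction to this one summary. The cost is a few lines of text and a small change to the derivation code; no data collection or other output changes.

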### **3. ANALYSIS AND REPORTING OUTPUTS**

All data collected will be listed and summarized as follows:

- Demographics and sleep history – Stage 1 and Stage 2 analysis sets
- Cancer history, medical treatment, co-morbidities – Stage 2 analysis set only
- ISI, EQ-5D-5L, FACT-ES – Stage 1 (day 0) and Stage 2 (day 0 and day 21) analysis sets
- Sleep diary, UEQ, AEs – Stage 2 analysis set only

#### **3.1. Patient Information**

##### **3.1.1. Disposition of Patients**

The number of participants who signed consent for each stage will be summarised as well as the number of patients within each analysis set (i.e. Stage 1 and 2 analysis set). In addition, the number of patients withdrawing early from the study and the reason why will also be summarised.

##### **3.1.2. Protocol Deviations**

Any protocol deviations recorded on the eCRF will be listed and summarised for each analysis set. Any deviations with a start date after the consent date for Stage 1 but prior to the consent date of Stage 2 will be considered as a deviation for Stage 1 of the study and summarised based on the Stage 1 analysis set. Any deviation reported on or after the consent date for stage 2 will be regarded as a Stage 2 deviation and summarised based on the stage 2 analysis set.

For summary purposes, deviations will be categorised as relating to:

- Informed consent
- Inclusion/exclusion criteria
- Study procedures
- Other

Statistical Analysis Plan for CLM-INS-004

Version: Final 2.0

Date: 9th September 2022

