## Statistical Analysis Plan for CLM-INS-004

Version: Final 2.0

Date: 9th September 2022**DOCUMENT REVISION HISTORY**

VERSION	DATE	AUTHOR/ UPDATED BY	COMMENTS
2.0	9 th September 2022	[name]	Amended definition of analysis sets to only include patient eligible for the study and added that baseline BMI would be reported

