## 2. ANALYSIS AND REPORTING CONSIDERATIONS

### 2.1. General Considerations

Statistical analysis will be performed using SAS® software. Continuous variables will be summarized using the mean, the standard deviation [SD], median, 25th and 75th percentiles, minimum value, and maximum value. Categorical variables will be summarized using frequency counts and percentages. Data will be listed in data listings.

Where applicable, 95% confidence intervals (CIs) will be presented.

The tables, listing and figures will be developed as a separate standalone document from the SAP. The document will provide templates of the outputs to be provided following database lock based on the summaries detailed in the SAP. All data will be listed, in addition to the summaries outlined in the SAP

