### 2.2. Definitions of Analysis Sets

The following analysis sets will be used in the statistical analyses and reporting of study data.

- Stage 1 analysis set will include all participants who consented to stage 1, are eligible for the study and have evaluable data for at least one of the questionnaires (ISI, EQ-5D-5L or FACT-ES).
- Stage 2 analysis set will be a subset of the Stage 1 analysis set and will include eligible Stage 1 participants who scored  $\geq 8$  on their baseline ISI questionnaire and consented to stage 2. Note if a patient consents to Stage 2 but does not provide **any** stage 2 data (e.g., questionnaire/sleep data) then they will be excluded from the stage 2 analysis set.

Statistical Analysis Plan for CLM-INS-004

Version: Final 2.0

Date: 9th September 2022

Note, listings will generally be based on the stage 1 analysis set with an indicator for patients who also entered into stage 2, with the exception of the cancer history, cancer treatment, co-morbidities, sleep diary, AE and UEQ listings which will be based on the stage 2 analysis set since these are only completed for stage 2 patients.

If a participant does not enroll in the digital diary (i.e., does not even download the app) but completes the UEQ, then data from the UEQ will not be included in the reporting of the data.

Percentages will generally be derived based on the analysis set N as the denominator, unless stated otherwise. Where there is missing data, % may be derived based on those within the analysis set who have evaluable data. Where applicable missing categories will be included to show the number of patients with missing data for the relevant endpoint.

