### 3.5. Adverse Events

The number of reported AEs in this study is expected to be low. Therefore, AE data will not be coded by MedDRA. Data will be listed as per the CRF entries.

Statistical Analysis Plan for CLM-INS-004

Version: Final 2.0

Date: 9th September 2022

The number and % of patient will be summarized for the following AE categories:

- Any AE
- Any SAE
- Any diary related AE (where “Possibly”, “Likely”, or “Definitely” is recorded for the AE relationship question on the eCRF)

AEs will be summarized based on the stage 2 analysis set only.

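### Deviation summaries and AE outputs run on eligible-only analysis sets, so Stage 1 eligibility breaches and AEs in Stage 1-ineligible diary users go uncounted; separately, the deviation date rule has a gap and an overlap

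*SAP*

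**What the plan says.** **Analysis sets.** The SAP revision history describes the version 2.0 change as "Amended definition of analysis sets to only include patient eligible for the study and added that baseline BMI would be reported". SAP 2.2 now reads "Stage 1 analysis set will include all participants who consented to stage 1, are eligible for the study", and adds a need for at least one evaluable questionnaire. The Stage 2 set "will be a subset of the Stage 1 analysis set". It also requires a baseline ISI of at least 8 and consent to Stage 2, and drops Stage 2 consenters who supply no Stage 2 data.

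**Deviations.** SAP 3.1.2 states: "Any protocol deviations recorded on the eCRF will be listed and summarised for each analysis set". One of its four summary categories is inclusion/exclusion criteria. Stage 1 deviations are "Any deviations with a start date after the consent date for Stage 1 but prior to the consent date of Stage 2". Stage 2 deviations are those reported on or after the Stage 2 consent date.

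**Adverse events.** SAP 3.5: "AEs will be summarized based on the stage 2 analysis set only". SAP section 3 says the same, and SAP 2.2 puts the AE listing on the Stage 2 set too. Protocol 9.2 has AEs recorded for everyone enrolled in Stage 2, and Protocol 10.3.3 presents all reported AEs and SAEs with no analysis-set limit.

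**Text pointing the other way.** SAP 2.1: "All data will be listed, in addition to the summaries outlined in the SAP". SAP 2.2 says only that listings are generally based on the Stage 1 set. SAP 3.1.1 reports how many people consented to each stage and how many are in each set, but not why anyone is outside a set.

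**The concern.** An eligible-only set is a defensible choice for a prevalence estimate. It does not suit an output whose purpose is to show how often ineligible people were enrolled, because the people to be counted have already been removed. A reader of the final report would see few or no Stage 1 eligibility deviations and could not tell whether enrolment was clean or the table could not show otherwise.

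Late discovery of a Stage 1 breach is realistic. Under Protocol 7.4.1 the team confirms cancer stage and other cancer diagnoses from medical records at the Stage 2 eligibility assessment. That comes after Stage 1 consent and questionnaires.

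The same restriction reaches safety. Safety of diary use is a stated secondary objective, and under Protocol 9.2 only SAEs judged directly related to the diary go to the sponsor. The AE table and listing are therefore where the remaining events would be seen.

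A further, independent problem is that the two date rules in SAP 3.1.2 use different kinds of date and different boundaries, so they do not divide deviations cleanly between the stages.

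**Working it through.** The plan states no figure for this point, so there is none to reproduce. The check applies the written rules to cases.

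**1. Eligibility breach, Stage 1 criterion** (for example, another cancer within the previous 5 years).
- Stage 1 set requires eligibility (SAP 2.2): the participant is out.
- Stage 2 set lies within the Stage 1 set (SAP 2.2): the participant is out.
- Deviation summaries run on these two sets (SAP 3.1.2): the breach is counted in neither.
- Deviation listing: omitted under 3.1.2, which lists by analysis set; included under the general statement in 2.1; left open by the word *generally* in 2.2. The SAP contradicts itself here.

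The row is near empty rather than certainly zero. A breach of a Stage 2 criterion, in someone who stays in the Stage 1 set, can still be entered under inclusion/exclusion criteria.

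**2. AE in the same participant, if they entered Stage 2 and used the diary.**
- AE table on the Stage 2 set (SAP 3.5): not counted.
- AE listing on the Stage 2 set (SAP 2.2): not listed.
- Protocol 9.2 and 10.3.3: recorded and presented.
- SAP section 4: declares that MedDRA coding is dropped and calls the sets a clarification, but does not say that AE reporting is narrowed.

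**3. Date rule.** Take Stage 1 consent as day 0 and, where given, Stage 2 consent as day 10. The Stage 1 rule is start date > day 0 and < day 10. The Stage 2 rule is report date ≥ day 10. Where there is no Stage 2 consent, the Stage 1 window is treated as open-ended.

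| Deviation | Stage 1 rule met | Stage 2 rule met | Falls in |
|---|---|---|---|
| Starts day 0, no Stage 2 consent | no | not applicable | neither |
| Starts day 0, reported day 1 | no | no | neither |
| Starts day 0, reported day 12 | no | yes | Stage 2 |
| Starts day −5, reported day 1 | no | no | neither |
| Starts day 5, reported day 5 | yes | no | Stage 1 |
| Starts day 5, reported day 12 | yes | yes | both |

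This affects participants inside the analysis sets as well as those outside. It would exist whatever version 2.0 had done to the sets.

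**4. Scale.** The plan expects 285 × 0.44 = 125.4, taken as 125, participants eligible for Stage 2 (Protocol 10.1, SAP 1.2.1). If all 125 consented, each one excluded would remove 1/125 = 0.8% of the AE denominator. As an assumption only, 0, 5 or 10 exclusions would remove 0%, 4% or 8%. The documents give no basis for choosing among these.

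**The case against.** The strongest reply is that little would be lost in practice. Records are screened before invitation (Protocol 7.2), and cancer stage and other cancers are checked again before Stage 2 (Protocol 7.4.1), so a Stage 1-ineligible diary user should be rare. Diary-related SAEs reach the sponsor within 24 hours whatever the analysis set (Protocol 9.3) and receive medical review (Protocol 9.5). Total exclusions from each set can be found by subtraction from the disposition table. This is a descriptive study of a diary that is not a medical device. All of that stands, and it keeps the point to reporting. It does not make the set-based counts right.

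Some stronger readings are tempting, but the documents do not support them:

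- *Deviations in excluded participants vanish from the report altogether.* This is certain only for the summaries. For the listing the SAP is contradictory.
- *Version 2.0 caused the consent-day gap, or introduced the condition on having data.* The gap comes from the date wording in SAP 3.1.2. The revision history credits version 2.0 with the eligibility condition only.
- *Failed day 21 calls go uncounted because of the set definition.* Protocol 7.4.5 sends them to the site deviation log, while SAP 3.1.2 covers deviations recorded on the eCRF. Nothing shows that they reach the eCRF.
- *Stage 2 entry with ISI below 8 is never counted.* That person stays in the Stage 1 set. If the breach starts inside the Stage 1 window, it is summarised there. The EDC also calculates the ISI total automatically.
- *AEs in Stage 2 consenters without diary or questionnaire data are lost.* SAP 2.2 gives those data types only as examples, so a recorded AE may itself count as Stage 2 data.
- *Self-reported eligibility makes this worse.* The self-reported items in Protocol 7.4.1 concern Stage 2 criteria. The Stage 2 set definition does not clearly exclude people who breach those, apart from the ISI threshold.

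On the date rule, it can be argued that the SAP meant *reported* loosely, as the date of occurrence. That removes the overlap, but then a consent-day deviation has no stage even if it is reported later.

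**Conclusion.** The concern holds in three limited parts:

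1. Stage 1 eligibility breaches are left out of the deviation summaries by construction, and the SAP conflicts with itself on whether they are listed.
2. AEs in a diary user later found Stage 1-ineligible are left out of both the AE table and the AE listing. This departs from the protocol, and SAP section 4 does not declare it.
3. The date rule leaves a consent-day deviation without a stage unless it is reported on or after Stage 2 consent. It also double-assigns a deviation that starts in the Stage 1 window and is reported on or after Stage 2 consent.

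The number of people or events affected cannot be derived from the documents and could be zero. Part 2 bites only if a Stage 1-ineligible person passes both record checks and enters Stage 2. The conclusion assumes that the set definitions and date rules are programmed as written. The prevalence estimate and the sample size are untouched. What is at stake is an honest count of eligibility breaches and a complete safety output.

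**What to change.** - **Deviations:** summarise and list them on everyone who consented to the relevant stage.
- **AEs:** base the tables and the listing on everyone who consented to Stage 2, with a flag for analysis-set membership.
- **Date rule:** use one date type, start or report, for both stages. Open the Stage 1 window on the Stage 1 consent date rather than after it, and say where anything dated earlier is to be placed.
- **Disposition (SAP 3.1.1):** give exclusions from each set by reason, separating ineligibility (by criterion) from absence of evaluable data.
- **SAP section 4:** declare the populations used for deviations and AEs.
- **Outcome analyses:** keep the version 2.0 sets.

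The cost is SAP wording and a different population flag in the deviation, AE and disposition outputs. No new data are needed. The one visible downside is that the report will show more deviations.
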